11 REPORTS

All reports to the Sponsor will be in English. The Sponsor will receive an electronic copy of all versions of the electronic CRFs.

11.1.1 Clinical Study Report

All clinical, analytical and statistical results will be presented in a clinical study report (CSR). The outline of this report will accord to the ICH-GCP E3 document "Structure and Content of Clinical Study Reports" of July 17, 1996.

The Sponsor will receive the original CSR.

All reports are the property of the Sponsor. Publication of the report or of part of it may only be allowed when authorized by the Sponsor in consultation with the clinical trial center.

11.1.2 Additional Reports

Within a year upon completion of the clinical trial, a summary of the CSR will be sent to the Ethics Committee and Competent Authorities as required by appropriated law.

Hospitalized: Severe disease	Hospitalized; Oxygen by NIV or High flow	6
	Intubation & Mechanical ventilation, $pO_2/FIO_2 \geq 150$ or $SpO_2/FIO_2 \geq 200$	7
	Mechanical ventilation $pO_2/FIO_2 < 150$ ($SpO_2/FIO_2 < 200$) or vasopressors	8
	Mechanical ventilation $pO_2/FIO_2 < 150$ and vasopressors, dialysis, or ECMO	9
Death	Dead	10

Notes:

1. If hospitalized for isolation only, record status as for ambulatory patient
2. If pO₂ not available, use SpO₂/FIO₂ ratio with a cutoff of 200

14 ANNEX 2

Remote/Video monitoring visit

Due to the Corona-Pandemic on-site monitor and pharmacy visits may not be possible due to travel restrictions and/or access restrictions at the hospitals. For this reason, a combined remote and video monitoring visits may be the only possibility to monitor the site for an indefinite period.

The general goals of the remote/video on-site monitoring visits are the same as for the on-site monitor visits with the restriction that complete source data verification is not possible. For the remote/video monitoring a software certified for the use in the medical field and GDPR conform (i.e., CLICKDOC Videosprechstunde for Germany and Austria) is used.

Monitoring will only be conducted within the limits of site personnel (availability, workload, time) and technical capabilities to ensure secure video monitoring. Furthermore, essential data have to be entered into the database (eCRF) which includes the upload of corresponding documents (e.g. laboratory, physician's letter) in order to perform SDV remotely.

Study sites need to agree with the remote and video monitoring. Therefore, a written confirmation document will be provided to the sites and needs to be signed and collected by the CRA.

The following data according to recommendations of the European authorities are to be checked via remote/video monitoring:

- Verification of availability and correctness of signed informed consent forms
- data relevant for the inclusion and exclusion (including medical history)
- doses and dose regimens of IMP
- recording of (serious) adverse events
- concomitant medication

Video Monitoring: documents will be shown to the CRA by videoconference.

The following data should be checked during an on-site Visits.

- For 100% of all randomized patients: verification of availability and correctness of signed informed consent
- For 100% of all randomized patients:
 - data relevant for the inclusion and exclusion
 - data relevant for the primary objective
 - data relevant for the secondary objectives
 - IMP treatment
 - concomitant medication
 - safety-related data for AEs / SAEs

Video Visits (blinded)

The following documents will be reviewed per Video-Monitoring if available, i.e. the site needs to have documentation on paper.

Categorie	Document
Informed Consent Form	ICF
Physician's letter/ Source Data Worksheets	In regard to I/E criteria, review of: 
 - Medical History - Concomitant Medication - Age, Weight, - Oxygen Saturation Safety:

	AE/SAE Documentation
Laboratory values	In regard to I/E criteria review of: ALT, bilirubin, Hb, Hepatitis B+C, HIV COVID positive testing

In case one of the listed documents is only available as an electronic patient file, it cannot be reviewed per video-monitoring.

Documents listed below for remote monitoring will also be checked within the frame of video monitoring visit.

Remote Visits:

General requirements for provision of scanned documents for remote monitoring:

- Quality of scans should have at least minimum 200 dpi.
- Completeness of documents will be guaranteed by on the cover page of the document the complete number of pages of the document is indicated (for example 1-12), with initials and actual date.
- No scans of documents including personal data or data which can lead to the identity of the patients will be provided.
- Study personnel will be instructed to send the scans as a response to an email of the CRA and to just respond to the email without adding another recipient to the email to avoid that documents will be sent to unauthorized third parties by mistake.
- Documents received by the study site will be documented in the monitoring report.

Remote Visits (blinded)

The following documents should be provided (in case of any changes to previous visit) by the sites upon request via email and checked by remote monitoring:

- Patient enrolment log
- Site delegation log
- IMP handover form
- IMP drug accountability form
- Trainings logs
- Acknowledgments (Protocol, IB)
- Site Visit Log
- Site staff documents (FD, GCP, CV)
- Note to files

Remote Visits (unblinded)

The following documents should be provided (in case of any changes to previous visit) by the sites upon request via email and checked by remote monitoring:

- Handover forms
- IMP dispatch form
- Preparation of trial medication (APN01 or Placebo)
- IMP accountability logs (APN01 or Placebo)
- Investigational product stock on site/ Pharmacy
- Temperature Recording Log (APN01 or Placebo)
- Training Logs
- Note to files
- Print out randomization confirmation eCRF

 4.7 Missing Values22

 4.8 Data Base Closure and Blind Data Review Meeting (BDRM)22

 4.9 Miscellaneous23

5 CHANGES FROM PROTOCOL25

6 SIGNATURES26

List of Abbreviations

In the following abbreviations are listed as used within this statistical analysis plan or which might occur within the tables, listings and graphs outputs:

AE	Adverse event
ATC	Anatomical therapeutic chemical
BDRM	Blind data review meeting
BID	bis in die, i.e. twice daily
BMI	Body mass index
CM	Concomitant medication
CRF	Case report form
CS	Clinically significant
DSMB	Data safety monitoring board
ECG	Electrocardiogram
eCRF	Electronic case report form
FAS	Full analysis set
IMP	Investigational medicinal product
LDH	Lactate dehydrogenase
MedDRA	Medical dictionary for regulatory activities
MH	Medical history
N	Number of patients
NCS	Not clinically significant
PE	Physical examination
PP	Per protocol set
PT	Preferred term
SAE	Serious adverse event
SAF	Safety analysis set
SAP	Statistical analysis plan
SAR	Serious adverse reaction
SD	Standard deviation
SOC	System organ class
SOFA	Sequential organ failure assessment
mSOFA	Modified sequential organ failure assessment
SUSAR	Suspected unexpected serious adverse reaction
TLG	Tables, listings, graphs
VFD	Ventilator-free days
WHO	World health organization
WHO-DD	World health organization drug dictionary

1 General

This Statistical Analysis Plan (SAP) was defined by the Sponsor and the responsible Statistician without knowledge of the randomization code. It is based upon the Study Protocol (version 7.0 of 10Aug2020) and contains detailed description of the statistical methods described therein.

The SAP describes prospectively the analyses to be performed on study data for final analysis. It was finalized prior to data base lock and unblinding.

This SAP serves as SAP for final analysis and includes relevant endpoints for final analysis only. Details of outputs are given in Appendix A.

The DSMB analyses are described in a separate 'SAP for DSMB'.

Methodology

This is a Phase II prospective, multi-centre, double-blind, randomized, placebo-controlled, interventional trial to assess clinical safety, tolerability, and efficacy of APN01 on top of best standard of care in patients with severe COVID-19 and to evaluate if treatment with APN01 on top of standard of care is superior to placebo (NaCl 0.9%) on top of standard of care.

Eligible patients will be centrally allocated using a dynamic randomization (1:1) at baseline (day 1) to Group A or B to receive the treatment or placebo. Dynamic randomization factors will be age in years (<65 years vs. ≥65 years), presence of at least one relevant co-morbid condition (hypertension, diabetes, coronary artery disease) for study protocol versions prior version 6.0 and center.

After screening at day -1 and randomization at day -1 or day 1, patients will be treated with APN01 or placebo intravenously twice daily (BID) every 12 hours (± 1 hour) over 3 to 30 minutes in the morning and in the evening until day 7 (14 doses). If a patient will be discharged from hospital before day 7 treatment can be stopped at day of discharge.

Periods and duration

The study will consist of three periods: screening (day -1), treatment period (day 1 to day 7) and follow-up period (day 10, day 14 and day 28). Study duration is up to 29 days per patient. Total study duration is up to 5 months, with 2-4 months recruitment period per country.

Number of patients planned

The planned sample size is 200 treated patients. Approximately 40 sites in Europe, Russia and US are planned, hence for a 1:1 (APN01:Placebo) randomization scheme. 186 patients (93 per group) will yield 80% power to detect a 20% absolute risk reduction in the primary composite endpoint, from 50% in the placebo group to 30% in the APN01 group at a two-sided alpha of 0.05. To consider patients who will be randomized but not treated a total of 200 patients (100 per group) will be enrolled.

DSMB Meetings

The regular DSMB will be performed after randomization of 8-10, 20, 50, 100 (if necessary), and 150 (if necessary) patients. Furthermore an ad hoc meeting of the DSMB may be called at any time by the DSMB Chair, coordinating investigator, medical monitor or sponsor imminent for any significant reason.

Study objectives

The primary study objective is to assess clinical efficacy of APN01 using a composite outcome of all cause-death or need of invasive mechanical ventilation up to 28 days.

The secondary study objectives are to assess efficacy of APN01 using log transformed levels of Lactate dehydrogenase (LDH) as a surrogate marker for organ damage, to evaluate the safety of APN01 in patients with severe COVID-19 and to monitor other biomarker changes (e.g. IL-6, Ang II) in patient with severe COVID-19 treated with APN01.

2 Efficacy and Safety Endpoints

2.1 Primary Efficacy Endpoint

The primary endpoint is a composite endpoint of all cause-death or invasive mechanical ventilation (up to 28 days or hospital discharge).

2.2 Secondary Efficacy Endpoints

The following secondary efficacy parameters will be analyzed:

- Log transformed levels of lactate dehydrogenase (LDH) at Day 5 as a surrogate marker for organ damage (powered secondary endpoint)
- 28-day mortality (all cause death)
- Ventilator-free days (VFD) (up to 28 days or hospital discharge)
- Proportion of responders, defined as ≥ 2 improvement in WHO's 11-Point Score system at Day 7, 10, 14 and 28
- Time to death (all cause)
- Proportion of patients with any use of invasive mechanical ventilation (up to 28 days or hospital discharge)
- Time to first use of invasive mechanical ventilation (up to 28 days or hospital discharge)
- Absolute values and absolute change in PaO₂/FiO₂ ratio over time
- Absolute values and absolute change in modified Sequential organ failure assessment score (mSOFA score) over time
- Time to a 2-point decrease in WHO's 11-Point Score system
- Absolute values and absolute change in lymphocyte counts over time
- Absolute values and absolute change in C-reactive protein levels over time
- Absolute values and absolute change in D-dimer over time
- Absolute values and absolute change in log transformed levels of LDH over time
- Time to hospital discharge
- Change in viral RNA over time

2.3 Safety Endpoints

- Adverse events (AEs) and serious adverse events (SAEs)
- Vital signs: Systolic blood pressure, Diastolic blood pressure, Heart rate, Body temperature, Respiratory rate
- Oxygen saturation
- Clinical laboratory assessments:
 - Biochemistry
 - Inflammatory indicators
 - Myocardial enzymes
 - Hematology
 - Coagulation
 - Urinalysis
 - Stool routine and occult blood

- ECG parameters: Heart rate [bpm], RR interval [ms], PR interval [ms], QT interval [ms], QRS complex [ms], ECG evaluation
- Detection of viral nucleic acid or viral gene sequencing

2.4 Biomarker Endpoints

- Angiotensin II (Ang II), Angiotensin 1-7 (Ang 1-7), Angiotensin 1-5 (Ang 1-5), Plasma-Renin-Concentration (PRC), Aldosterone, Angiotensin-converting enzyme 2 (ACE2) activity and concentration, Angiotensin I (Ang I), Angiotensin 1-9 (Ang 1-9)
- Cytokines: Interleukin 6 (IL-6), Interleukin 8 (IL-8), soluble Tumor Necrosis Factor receptor type II (TNFR-II), Plasminogen Activator Inhibitor type-1 (PAI-1), von Willebrand factor (vWF-A2), Tumor necrosis factor- α (TNF- α)
- Alveolar epithelial markers: soluble Receptor for Advanced Glycation End products (RAGE), Surfactant protein-D (SP-D)
- Endothelial markers: Angiopoietin-2
- Change in clinical laboratory markers associated with poor outcome over time (e.g., lymphocyte counts, D-Dimer, CRP, hsTnI (high sensitivity troponin))
- NT-proBNP, Ferritin
- Immune function and COVID-19 antibodies
- Serology

3 Statistical Analysis Sets

3.1 Full Analysis Set (FAS)

The full analysis set (FAS) includes all randomized patients.

3.2 Safety Analysis Set (SAF)

The safety analysis set (SAF) consists of all randomized patients who received study medication (independent of whether it is APN01 or Placebo). If the application of any study medication is not certain, the patient will be included in the SAF.

3.3 Per-Protocol Analysis Set (PP)

The PP includes all subjects included in the SAF who had no major protocol deviations and completed through Day 28 or until discharge from the hospital (end of study follow-up). Protocol deviations will be identified and classified for each subject during a blind data review meeting (BDRM) (see section 4.8).

The following protocol deviations are a priori defined to have a “major” grade and will lead to an exclusion from the PP set:

- ❑ Informed consent procedure: ICF not signed and dated by patient/investigator
- ❑ Violation of an in- or exclusion criterion
- ❑ Randomization procedure
- ❑ Incorrect use of IMP (storage, preparation and administration)
- ❑ Use of forbidden concomitant medication
- ❑ Delayed reporting of serious adverse events

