8.3.3.4 Study Termination

Individual study completion is defined as patients having finished the treatment period without early termination and reached the last visit within the specified window per the study schedule (Day 28; Table 1).

Overall End of Study is defined as the date of last patient last visit (LPLV). Within 90 days after the End of Study the Coordinating Investigator and the Sponsor must inform regulatory authorities and ethics committees about the completion of the trial.

The Sponsor may terminate the trial at any time for any reason and in particular if serious safety concerns rise for the patients. In the case of study termination, participating sites will be informed of the procedures to be followed to ensure that adequate consideration is given to the protection of the patient's safety.

The Sponsor has to inform the CAs and the ECs within 15 days.

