8.5.2.2.12 Patient status assessment

Patient status assessments includes the documentation of the following: no change, discharge from hospital, transition to critical illness, and death.

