8.7.1.2 Eligibility for Statistical Evaluation

Eligibility of patients will be determined within the data review meeting (blind data review meeting, DRM).

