8.7.1.2.3 Per-Protocol Analysis Set (PP)

The PP includes all subjects included in the SAF who had no significant protocol deviations and completed through Day 28 or until discharge from the hospital (end of study follow-up). The PP will only be analyzed for main efficacy outcome measures (as treated).

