4.4.1 Analysis of Primary Efficacy Endpoint

The primary endpoint is a composite endpoint of all cause-death or invasive mechanical ventilation (up to 28 days or hospital discharge).

The following null hypothesis will be tested:

- $H_0: p_{APN01} = p_{Placebo}$

versus the alternative

- $H_1: p_{APN01} \neq p_{Placebo}$

H_0 will be tested using a Chi-squared test. The level of significance is 5% (two-sided). In addition, logistic regression analyses will be conducted considering additional co-factors.

All cause-death

The percentage of patients who have died at Day 28 will be presented by treatment group.

Patients with death from any cause will be used for this endpoint as part of responder. Patients who are still alive at Day 28 will be considered as non-event.

The following cases may occur:

- Patient discharged from hospital **and** discontinued before Day 28, will be followed up by telephone interview to check whether they are alive or dead, if unclear as no telephone interview available, death is assumed (worst case) at last available date of early termination, hospitalization or hospital discharge
- No discharge from hospital, **but** early discontinuation before Day 28 will be followed up by telephone interview to check whether they are alive or dead, if unclear as no telephone interview available, death is assumed (worst case) at date of early termination
- Discharged from hospital, **but** no discontinuation before Day 28: No telephone interview, but regular entry at Day 28 about alive/death status

Invasive mechanical ventilation (up to 28 days or hospital discharge)

Invasive mechanical ventilation is defined as patients who are intubated or have a tracheostomy tube and are receiving positive pressure ventilation. Patients with at least one invasive mechanical ventilation (event with type of ventilation 'Mechanical ventilation') up to 28 days or hospital discharge will be used for this endpoint as part of responder.

Chi-squared test

Proportion of responder, i.e. those patients that died or having an invasive mechanical ventilation (up to 28 days or hospital discharge), as well as the p-value (two-sided) will be reported.

Logistic regression

A logistic regression with the responder (yes/no) as independent variable will be applied.

The following co-factors will be included in the logistic regression:

- Arterial hypertension

- ❑ Diabetes
- ❑ Coronary artery disease
- ❑ Age (<65 years vs. >=65 years)
- ❑ Center

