The odds ratio along with its associated 95% confidence intervals will be reported.

Ventilator-free days (VFD) (up to 28 days or hospital discharge)

VFD will be calculated as follows:

$VFD = \text{maximum}((\text{Duration in the study [days]} - \text{Duration of ventilation [days]}); 0)$

i.e. if the duration of ventilation is greater than the duration in the study, VFD is set to 0.

Duration in the study [days] = Date of study completion/ discontinuation - Date of randomization + 1.

Patients who died before or on Day 28 will be censored at the day before death (Date of death - 1).

Duration of ventilation [days] = Sum of days with all required ventilations.

If ventilation started before randomization, the duration will be counted from the date of randomization. If ventilation started and/or ended after study completion/ discontinuation, the duration will be counted until date of study completion/ discontinuation.

If ventilation is ongoing and/or no stop date is available, the duration will be calculated until date of study completion/ discontinuation or date of death respectively.

VFD will be analyzed for both all patients as well as for the subgroup of patients who were alive at Day 28 or hospital discharge/early termination. For the analysis of all patients separate analyses will be conducted for patients who died: a) VFD will be set to 0, b) the observed VFD until death will be considered.

Summary tables will be generated by treatment group.

VFD will be compared using Wilcoxon rank sum test at a significance level of 5% (two-sided) and p-value (two-sided) will be reported.

In addition, bootstrap methods will be applied to calculate 95% confidence intervals and two-sided p-values for the difference in means between treatment groups.

Proportion of responders, defined as >= 2 improvement in WHO's 11-Point Score system at Day 7, 10, 14 and 28

Patients who will be not assessed from any cause (e.g. discharge from hospital, early termination, death or in-home visit) will be considered as non-responder.

Chi-squared test or Fisher's exact test

Proportion of responder, i.e. those patients that have >= 2 improvement in WHO's 11-Point Score system, as well as the p-value (two-sided) will be reported for Day 7, 10, 14 and 28.

Logistic regression

The following co-factors will be included in the logistic regression:

- ❑ Arterial hypertension
- ❑ Diabetes
- ❑ Coronary artery disease

- Age (<65 years vs. ≥65 years)
- Center

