4.8 Data Base Closure and Blind Data Review Meeting (BDRM)

A data base closure will be performed prior to the analysis. All parameters will be checked, as specified in the data validation plan, and all queries resolved before data base closure and analysis.

A data review will be conducted prior to unblinding based on all data to check for protocol deviations and to allocate the patients to the analysis sets. At least the following items will be discussed:

- Informed consent procedure: ICF not or too late signed and dated by patient/investigator
- Violation of any in- or exclusion criterion
- Randomization procedure
- Incorrect use of IMP (storage, preparation and administration)
- Use of forbidden concomitant medication
- Delayed reporting of serious adverse events

These evaluations and assessments will be done together and in agreement with the Sponsor, however FGK in cooperation with CTC North will provide the Sponsor with the appropriate patient listings (as defined in Appendix A). Data review can be done via a telephone conference or in writing.

The affiliation of subjects to the SAF, FAS, and the PP set will be done prior to unblinding.

Data unblinding will be done after data base closure / data review. The unblinded data including formats will be provided from CTC North to FGK for final analysis.

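### Read literally, the per-protocol set leaves out observed in-hospital deaths before Day 28, which are primary events, and it also drops patients for late SAE reporting

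*SAP*

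**What the plan says.** SAP 3.3 admits to the PP set patients of the safety set "who had no major protocol deviations and completed through Day 28 or until discharge from the hospital". Protocol 8.7.1.2.3 has the same condition: patients "who had no significant protocol deviations and completed through Day 28 or until discharge from the hospital (end of study follow-up"). Both texts carry that bracketed gloss, and neither has a clause for death.

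Death is a component of the primary composite. SAP 4.4.1 states: "Patients with death from any cause will be used for this endpoint as part of responder". SAP 3.4 makes the full analysis set (FAS, all randomized patients) the primary efficacy set. It uses the PP set, as treated, only for the main efficacy outcomes, which I take to include the primary composite.

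Membership is settled at a blind data review. SAP 4.8 has it held before unblinding "to check for protocol deviations and to allocate the patients to the analysis sets", and protocol 8.7.1.2 says: "Eligibility of patients will be determined within the data review meeting". Neither gives a rule for patients who died.

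SAP 3.3 then lists the deviations that are major in advance and lead to exclusion from the PP set. One of them is late reporting of an SAE. Protocol 9.1 also lists it as major, but the automatic exclusion is in the SAP. The reporting limit, in protocol 8.5.2.2.13.2.1, is 24 hours from first awareness.

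**The concern.** A PP analysis should show whether the result depends on departures from the protocol. Here two entry rules depend on how the patient fared.

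A patient who dies in hospital on day 12 has reached neither Day 28 nor discharge. If the text is applied as it stands, that patient leaves the PP set although the death is one of the events the analysis is meant to count. What remains is mainly ventilation among patients who survived to discharge or Day 28. The PP and FAS results could then differ for a reason unrelated to adherence, and the gap could be misread as an adherence effect. If the blind review decides case by case instead, membership rests on a choice that was not pre-specified.

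The late-SAE rule is a smaller case of the same fault. Only a patient with an SAE can be removed by it, and death is itself a seriousness criterion (protocol 8.5.2.2.13.2.2). What it measures is how quickly the site reported.

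**Working it through.** **1. Does completion include death?**

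- Protocol 8.3.3.4: "Individual study completion is defined as patients having finished the treatment period without early termination and reached the last visit". A patient who dies in hospital earlier does not meet this. It is not the PP criterion itself, because the PP set also accepts discharge.
- Protocol 8.5.2.2.12 lists the patient statuses as "no change, discharge from hospital, transition to critical illness, and death", so discharge and death are separate.
- SAP 4.4.2, on ventilator-free days: "the duration will be calculated until date of study completion/ discontinuation or date of death respectively". Death is named apart from completion, and equally apart from discontinuation.
- SAP 4.4.2, on time to discharge, gives one censoring rule for patients who completed or stopped early and another for patients who died.

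Where the SAP wants a rule for death it writes one, and SAP 3.3 has none. There is also an asymmetry. Under SAP 4.4.1 a patient who is discharged, then discontinued, with unknown status is assumed dead. That patient can still enter the PP set through discharge, so an assumed death may count while an observed in-hospital death does not qualify.

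**2. The plan's own figure.** Inputs from protocol 8.7.2: 50% vs 30%, two-sided alpha 0.05, power 80%, chi-squared test. With pooled variance and no continuity correction:

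n per group = [1.960 × √(2 × 0.4 × 0.6) + 0.842 × √(0.25 + 0.21)]² / 0.20² = 93

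The stated 93 per group reproduces (power 0.800) and is not in dispute. The planned odds ratio is (0.30/0.70)/(0.50/0.50) = 0.43.

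**3. Literal exclusion of in-hospital deaths.** Let p be the composite rate in an arm and d the proportion of that arm's patients who die in hospital before Day 28.

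PP rate = (p − d)/(1 − d); PP odds = (p − d)/(1 − p)

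The documents do not split the composite, so every d is an assumption. If deaths are the same share s of events in both arms, d = s × p. The factor (1 − s) then cancels and the odds ratio stays at 0.43.

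| Assumption | Placebo | APN01 | Difference | Odds ratio |
|---|---|---|---|---|
| No exclusion | 50.0% | 30.0% | 20.0 points | 0.43 |
| s = 20% in both arms | 0.40/0.90 = 44.4% | 0.24/0.94 = 25.5% | 18.9 points | 0.43 |
| s = 66% in both arms | 0.17/0.67 = 25.4% | 0.102/0.802 = 12.7% | 12.7 points | 0.43 |
| d = 30% vs 10% | 0.20/0.70 = 28.6% | 0.20/0.90 = 22.2% | 6.3 points | (0.20/0.70)/(0.20/0.50) = 0.71 |
| d = 20% in both arms | 0.30/0.80 = 37.5% | 0.10/0.80 = 12.5% | 25.0 points | (0.10/0.70)/(0.30/0.50) = 0.24 |

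In the last two rows deaths are unequal shares of events: 0.30/0.50 = 60% vs 0.10/0.30 = 33%, and 0.20/0.50 = 40% vs 0.20/0.30 = 67%. In the first of these the whole effect is on death and the PP set largely hides it. In the second the whole effect is on ventilation and the PP set enlarges it.

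**4. Late SAE reporting.** Assume a fraction q of event patients, and nobody else, is removed, equally in both arms. PP rate = p(1 − q)/(1 − pq).

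- q = 10%: 0.45/0.95 = 47.4% vs 0.27/0.97 = 27.8%, difference 19.5 points.
- q = 30%: 0.35/0.85 = 41.2% vs 0.21/0.91 = 23.1%, difference 18.1 points.

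The odds ratio is again 0.43.

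**The case against.** The best reply is that the clause was written to drop withdrawn and lost patients, and that its gloss about the end of follow-up takes in patients followed until they died. Several places support this. Protocol 8.7.1.2.4 assumes that nobody will discontinue before Day 28 or discharge, yet the trial plans for 30% to 50% of patients dying or being ventilated; that fits only if dying is not early discontinuation. Protocol 8.3.3.1 does not name death among its reasons for drop-out, though its list is not exhaustive. Where the authors want survivors only, as in one ventilator-free-days analysis, they say so. SAP Appendix A, which defines the review listings, is not among the documents. This makes the inclusive reading possible, perhaps the intended one, but no visible text states it.

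It can also be said that allocation before unblinding cannot be steered by treatment arm. That is right, and it limits the harm of a case-by-case decision. It does not make the rule pre-specified.

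Two stronger inferences should be resisted. A reader might conclude that the primary result is biased; it is not, because the FAS keeps every randomized patient. A reader might also take the 53% in protocol 6.1 as the death share. That figure is fatality among ventilated patients in a UK cohort. The formula needs in-hospital deaths as a share of all death-or-ventilation events, which is a different quantity in a different population.

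**Conclusion.** The point holds in a limited form. On the literal text, observed in-hospital deaths before Day 28 do not qualify for the PP set, and late SAE reporting removes patients for a reason tied to outcome and to the site. Both rules select on outcome-related events. The documents do not show that the review would in fact exclude the deaths, nor in which direction the PP result would move.

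The FAS analysis, the sample size and the type I error are unaffected. Deaths after discharge, and ventilated patients who reach discharge or Day 28, stay in the PP set. The shift from 20 points to between 18.9 and 12.7 assumes an equal death share of 20% to 66%, a range with no source in the documents. The 6.3 and 25.0 points come from two constructed cases and show only that either direction is possible. The late-SAE effect is smaller: 0.5 to 1.9 points under its own assumption. The change should be made because it is nearly free and replaces an outcome-dependent or discretionary set with a stated one.

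**What to change.** - In SAP 3.3, replace the completion condition with: *followed through Day 28, hospital discharge or documented death, whichever comes first*. Add that a death assumed only because status is unknown (SAP 4.4.1) does not count as completion. Without that limit, patients lost in hospital would enter the PP set as events. The discharge route stays as it is.
- In SAP 3.3, take late SAE reporting off the list of excluding deviations, and word the general condition as no major deviation other than this one. Keep it as a reported major deviation, in line with protocol 9.1.
- Record both as changes from the protocol in SAP section 5, before unblinding.

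The cost is two short edits and two entries in section 5. No new data are needed, since vital status is already collected for the primary endpoint. The SAP was signed on 11 January 2021, and the documents do not show whether the blind review has taken place, so the timing needs to be checked.
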